Currently, there is a paucity of prospective data studying the use of SBRT for bone metastases originating from low alpha-beta tumors, with systematic reporting of changes in pain scores and analgesia use over time. The vast majority data looking at SBRT in bone lesions focuses on local control and survival, rather than more tangible outcomes in a palliative population including symptomatic control, durability of response (and need for retreatment), and patient reported quality of life; a component that is understudied in this group despite its tremendous value. Furthermore, SBRT for bone metastases has yet to become common practice given the limited evidence for its efficacy and uncertainty in regards to toxicity.

We propose an investigation of the potential benefits of SBRT for symptomatic bone metastases in patients with prostate cancer, breast cancer, RCC, melanoma, and sarcoma. We look to conduct a prospective cohort study (SOLAR-P) that is adequately powered to analyse efficacy in alleviating pain from bone lesions and compare this to well-established rates in literature for conventionally fractionated palliative RT. We will also assess the tolerability of this modality, toxicity rates, and effect on quality of life. If our results show that SBRT has a significant benefit on this population, the goal would be to pursue a larger randomized trial to confirm the findings.

Methods

Patient Population:

Patients will be accrued from the Juravinski Cancer Centre. Eligibility will be determined based on the criteria listed below, and informed consent will be established.

- Inclusion
 - Diagnosis of prostate cancer, breast cancer, renal cell carcinoma, or melanoma
 - Radiographic evidence of bone metastases requiring treatment for pain
 - BPI score of ≥ 2
- Exclusion
 - Spinal lesions
 - Severe or progressive neurological deficit
 - Impending (Mirels' score ≥ 9) or existing pathological fracture
 - Bone metastasis in a previously irradiated site
 - Active concurrent systemic therapy
 - > 5 lesions requiring treatment
 - Lesions > 5 cm in largest diameter
 - Life expectancy < 3 months
 - Age < 18
 - KPS < 50
 - Unable to provide informed consent

Primary Outcome:

- **Overall Pain Response at 3 months:** Assessed using the Brief Pain Inventory (BPI; Appendix A) and converting daily analgesic use to oral morphine equivalent (OME)
 - *Complete response* defined as BPI pain score of 0 with no increase in OME.

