Enrolled patients will receive the study dose of 15 to 20 Gy in 1 fraction to all painful bony lesions with SBRT. Planning and delivery will be conducted using a volumetric modulated arc therapy (VMAT) approach on our Varian Truebeam platform. Patients will be CT simulated, with a vac-lock immobilization. Use of 4DCT will be dependent on the area being treated. The gross tumor volume (GTV) will be defined as the visible abnormality based on CT imaging. The planning target volume (PTV) will be an additional 5 mm in all directions. The SBRT prescription will ensure that at least 95% of the PTV will be covered with the prescribed dose, and that at least 99% of the PTV will be covered by 95% of the prescription dose. Dose to organs at risk will be based on institutional guidelines for single fraction SBRT. Daily image guidance will be performed using cone beam CT aligning to relevant bony anatomy +/- PTV if visible.

Evaluation During Study:

The primary outcome will be overall pain response, measured using the BPI. Patients will be assessed using the BPI at baseline, and then at 1 month, 3 months, and 6 months following the completion of the SBRT treatment course. Responses will be obtained by patient self-reported questionnaires in clinic or by telephone follow-up. The sum of responses will dictate the overall response to treatment. Patients will be seen once for treatment review during their SBRT course to document acute toxicity. They will also be assessed at the 1 month, 3 month, and 6 month intervals to record acute and late toxicity using CTCAE version 5.0. Quality of life will be measured using the EORTC QLQ-C15-PAL and BM22 questionnaires at the same timepoints.

Sample Size and Statistical Analysis

Sample size:

The estimated pain response at 3 months using cRT is approximately 60% (null hypothesis is that SBRT will have a response of 60% as well). However, we postulate that the pain response at 3 months using SBRT will be 80% (alternative hypothesis). Given 80% power, two-sided alpha of 0.05, we will require 41 patients to test this hypothesis using a one sample binomial test. We plan to recruit 45 patients to account for any losses to follow-up.

Statistical Analysis:

The observed proportion of pain response at 3 months with SBRT will be compared to the null value of 0.6 using a one sample binomial test. The corresponding 95% confidence interval (CI) around the observed proportion will be calculated using the Wilson score method.

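### If the one-sample binomial test is exact, 41 evaluable patients give 70.4% power, not 80%, and the Wilson interval is not its counterpart

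*Protocol*

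**What the plan says.** In the Protocol, under Sample Size and Statistical Analysis (Sample size), the null rate is set by "The estimated pain response at 3 months using cRT is approximately 60% (null hypothesis is that SBRT will have a response of 60% as well" and the alternative by "we postulate that the pain response at 3 months using SBRT will be 80% (alternative hypothesis". The size follows: "Given 80% power, two-sided alpha of 0.05, we will require 41 patients to test this hypothesis using a one sample binomial test", and then "We plan to recruit 45 patients to account for any losses to follow-up".

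Under Statistical Analysis in the same section, the observed 3-month response "will be compared to the null value of 0.6 using a one sample binomial test". The interval is also fixed: "The corresponding 95% confidence interval (CI) around the observed proportion will be calculated using the Wilson score method".

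The Background describes "a prospective cohort study (SOLAR-P) that is adequately powered to analyse efficacy in alleviating pain from bone lesions" and gives the next step: "If our results show that SBRT has a significant benefit on this population, the goal would be to pursue a larger randomized trial".

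The text does not say whether the test is exact or a score (normal) test, and it gives no critical number of responders.

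**The concern.** The protocol fixes sample size, power, alpha, the name of the test and the interval method together, so they can be checked against one another. A binomial test ordinarily means the exact test, and the Wilson interval belongs to a different one: it is the inversion of the score test without continuity correction. The exact test is more conservative at this size, so two things could go wrong.

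- The stated 80% power may not be delivered at 41 evaluable.
- The p-value and the interval that is said to correspond to it may give opposite answers. If the form of the test were chosen after such a result, the choice would decide the conclusion.

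At stake are the claim of adequate power and the meaning of a significant benefit, on which the protocol rests its aim of a larger randomized trial.

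**Working it through.** **Inputs** (Protocol, Sample Size and Statistical Analysis): p0 = 0.6, p1 = 0.8, two-sided alpha 0.05, power 80%, 41 required, 45 recruited. The implied allowance for loss is 4/45 = 8.9%; no loss rate is stated.

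**1. The plan's own figure.** The arcsine formula is n = [(1.960 + 0.842) / h]², with h = 2·arcsin√0.8 − 2·arcsin√0.6 = 2.2143 − 1.7722 = 0.4421. This gives n = 40.15, rounded up to 41. The normal formula with null and alternative variances gives [(1.960·√0.24 + 0.842·√0.16) / 0.2]² = 42.04, rounded up to 43. So 41 is reproduced by a standard approximation.

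**2. Exact test at 41.** With X ~ Bin(41, 0.6):
- P(X ≥ 31) = 0.02736, which is above 0.025
- P(X ≥ 32) = 0.01177
- P(X ≤ 17) = 0.01257
- P(X ≤ 18) = 0.02701

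The equal-tailed test rejects at X ≤ 17 or X ≥ 32, with size 0.01257 + 0.01177 = 0.0243. The minimum-likelihood version rejects at X ≤ 18 or X ≥ 32, with size 0.02701 + 0.01177 = 0.0388. Success needs at least 32 in both, so power is P(X ≥ 32 | 0.8) = 0.704. A continuity-corrected score test has the same upper cut-off and power.

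**3. Uncorrected score test at 41.** It rejects upward when X ≥ 24.6 + 1.960·√(41·0.6·0.4) = 30.75, that is at 31 or more. Power is P(X ≥ 31 | 0.8) = 0.818. The lower region is X ≤ 18, so the true two-sided size is 0.02701 + 0.02736 = 0.0544, of which the upper tail is 2.7% against a nominal 2.5%.

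**4. The outcome 31/41 (75.6%).**
- Exact p: 2 × 0.02736 = 0.055 equal-tailed, 0.054 minimum-likelihood. Neither rejects.
- Score: z = (31 − 24.6)/√9.84 = 2.04, p = 0.041. It rejects.
- Wilson 95% interval: 60.7% to 86.2%, excluding 60%.
- Clopper-Pearson 95% interval: 59.7% to 87.6%, including 60%.

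P(X = 31 | n = 41) is 11.4% at a true 80% and 1.6% at a true 60%.

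**5. All evaluable counts from 41 to 45.** Success cut-off and power at a true 80%:

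| Evaluable | Exact equal-tailed | Score | True two-sided size, score |
|---|---|---|---|
| 41 | ≥32, 70.4% | ≥31, 81.8% | 5.4% |
| 42 | ≥32, 79.5% | ≥32, 79.5% | 3.9% |
| 43 | ≥33, 77.1% | ≥33, 77.1% | 4.2% |
| 44 | ≥34, 74.6% | ≥33, 84.6% | 6.4% |
| 45 | ≥34, 82.6% | ≥34, 82.6% | 4.7% |

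The minimum-likelihood exact test has the equal-tailed test's cut-offs except at 44, where it needs 33 or more (power 84.6%, size 4.55%). In the direction of benefit, an exact test and the Wilson interval disagree at only two outcomes: 31/41 (both exact versions) and 33/44 (equal-tailed only: p = 0.055, Wilson lower limit 60.6%). The equal-tailed exact test with Clopper-Pearson, and the score test with Wilson, agree at every count from 41 to 45 evaluable.

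**The case against.** The strongest reply is that the text has a coherent reading. It calls the Wilson interval the corresponding one, and the Wilson interval corresponds to the uncorrected score test. On that reading 41 gives 81.8% power and test and interval cannot disagree. The form of a test is also a detail often left to the SAP, which is not at hand. This has real weight: it makes the finding conditional. It does not remove it, because the protocol itself ties 80% power and 41 patients to a test whose usual meaning is exact, and nothing in the text rules that meaning out.

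A reader might infer more than the protocol supports:

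- *That 41 is an arithmetic error.* It is not; the arcsine formula gives it.
- *That both readings fail equally.* They do not. The exact reading loses about 10 points of power. The score test is run at a nominal 0.05 and exceeds it by 0.4 points through discreteness.
- *That the trial has an 11.4% chance of a contradictory report.* That figure is conditional on exactly 41 evaluable and a true 80%. With no stated loss rate the unconditional chance is unknown, and smaller.
- *That the randomized trial turns on one responder.* The protocol calls it a goal, not a decision rule.

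It is also fair to object that restating power does not create it: under the exact test any single loss takes power below 80%. Holding 45 evaluable at the implied 8.9% loss would need 45/(41/45) = 49.4, about 50 recruited. That is open to the sponsor, but it is not needed to make the protocol consistent.

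**Conclusion.** The point holds conditionally and should be fixed. If the exact test is meant, stated power is about 10 points too high at 41 evaluable (70.4%, a 29.6% chance of missing a true 80% rather than 20%), and the Wilson interval can contradict the test at 31/41. If the uncorrected score test is meant, sample size and interval fit together and what remains is minor (true size 5.4%, upper tail 2.7%).

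The conclusion assumes that patients lost to follow-up leave the denominator. The recruitment allowance suggests this, but the section does not state it. If all 45 are evaluable, or losses stay in the denominator as non-responders, the cut-off is 34 of 45 under the exact and score tests alike, and test and interval do not disagree in the direction of benefit. The 82.6% power applies when all 45 are evaluable; counting losses as non-responders would change it.

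**What to change.** Keep 45 recruited. Before outcome data are seen, name one test with its matching interval and replace the single power statement with cut-offs and power for 41 to 45 evaluable. Either:

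(a) Exact equal-tailed binomial test against 0.6 with the Clopper-Pearson 95% interval: success at ≥32 / 32 / 33 / 34 / 34 responders and power 70.4 / 79.5 / 77.1 / 74.6 / 82.6% with 41 / 42 / 43 / 44 / 45 evaluable; or

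(b) Score test without continuity correction against 0.6 with the Wilson 95% interval: success at ≥31 / 32 / 33 / 33 / 34, power 81.8 / 79.5 / 77.1 / 84.6 / 82.6% and true two-sided size 5.4 / 3.9 / 4.2 / 6.4 / 4.7%.

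Option (b) is the smaller edit, since it keeps both 41 and the Wilson interval.

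The cost is wording only, with no extra patients. Under (a) the stated power is less favourable and falls below 80% after any loss. Under (b) the protocol discloses a true size above 0.05 at 41 and 44 evaluable and power below 80% at 42 and 43.

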Appendix A. Brief Pain Inventory

Date: / /
 (month) (day) (year)

Study Name: _____

Subject's Initials : _____

Protocol #: _____

Study Subject #:

PI: _____

Revision: 07/01/05

[figure not shown]
PLEASE USE
BLACK INK PEN

Brief Pain Inventory (Short Form)

1. Throughout our lives, most of us have had pain from time to time (such as minor headaches, sprains, and toothaches). Have you had pain other than these everyday kinds of pain today?

Yes No

2. On the diagram, shade in the areas where you feel pain. Put an X on the area that hurts the most.

3. Please rate your pain by marking the box beside the number that best describes your pain at its **worst** in the last 24 hours.

0 1 2 3 4 5 6 7 8 9 10
 No Pain Pain As Bad As You Can Imagine

4. Please rate your pain by marking the box beside the number that best describes your pain at its **least** in the last 24 hours.

0 1 2 3 4 5 6 7 8 9 10
 No Pain Pain As Bad As You Can Imagine

5. Please rate your pain by marking the box beside the number that best describes your pain on the **average**.

0 1 2 3 4 5 6 7 8 9 10
 No Pain Pain As Bad As You Can Imagine

6. Please rate your pain by marking the box beside the number that tells how much pain you have **right now**.

0 1 2 3 4 5 6 7 8 9 10
 No Pain Pain As Bad As You Can Imagine

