Retreatment with palliative RT has also been shown to be effective following no response or symptomatic relapse after initial treatment. In the per-protocol analysis, the SC20 trial reported that patients retreated with 8 Gy/1 fraction and 20 Gy/5 fractions had pain response rates of 45% and 51%, respectively at 2 months post-treatment (12). Overall, 48% of patients who received their assigned treatment had reduced pain at the site of repeat radiation, regardless of whether or not they responded to their initial treatment. In addition, 68% had improved quality of life pain scores.

SBRT has shown promising early results in the management of bone metastases. In addition to its utility in spinal lesions, SBRT has been reported to improve local control in prostate cancer bone metastases with reductions of in-field failure in comparison to hypofractionated schedules (13), but it was unclear whether this translated into long term pain relief. Also, there has been some research in the use of SBRT in RCC bone metastases, given its resistance to conventional fractionation. One study showed that SBRT improved symptom control rates at 10, 12 and 24 months in comparison to standard external beam RT, with a median time to control of 2 weeks (14), but documentation of pain control was variably captured, and largely extrapolated from clinical notes. Other retrospective data in RCC, melanoma and sarcoma suggested a high degree of pain relief in patients treated with SBRT for spine metastases, however pain scores were not prospectively captured (15), and the study was likely to be underpowered to determine a significant effect. In addition, a recent phase II randomized trial that included patients with bone metastases from all disease sites (majority lung), showed that single fraction SBRT had higher rates of pain response at 2 weeks and 3 months compared to conventional fractionation (16). However, the degree of pain response in the control group was less than expected, the majority of the patients on this study did not have low alpha-beta tumors, and the radiation dose schedule in the conventional arm was not typical of standard practice (30 Gy in 10 fractions as compared to 8 Gy/1 fraction or 20 Gy/ 5 fractions).

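### The BPI score behind the primary endpoint is not tied to the SBRT-treated lesions, so pain elsewhere that crosses a threshold can change a patient's response class

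*Protocol*

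**What the plan says.** The Background section of the protocol describes a study "adequately powered to analyse efficacy in alleviating pain from bone lesions". Under Treatment Plan, SBRT is given "to all painful bony lesions with SBRT".

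Under Evaluation During Study, "The primary outcome will be overall pain response, measured using the BPI". Complete response, under Primary Outcome, is "defined as BPI pain score of 0 with no increase in OME". Partial response needs a BPI drop of at least 2 without more OME, or no BPI rise with an OME reduction of at least 25%. Failure includes a BPI rise of at least 2, an OME increase above 50%, re-irradiation, or pathologic fracture. None of these criteria names a treated site or index lesion, and none says how to score new pain elsewhere.

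In Appendix A, items 3 and 4 begin "Please rate your pain by marking the box beside the number that best describes your pain at its". Item 5 is worded almost the same way, and item 6 asks about present pain. Item 1 sets aside only everyday pains: "Have you had pain other than these everyday kinds of pain today". Item 2 asks for location: "On the diagram, shade in the areas where you feel pain", with a cross on the worst area. No response rule uses that diagram.

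**The concern.** The question concerns the treated lesions, while the score covers the whole body. Treating every bone lesion that is painful at entry deals with bone pain present at that time. It does not deal with new bone lesions by month 3, or with non-bone pain at any time. The eligibility criteria make such pain plausible: metastatic disease, up to 5 lesions requiring treatment, KPS down to 50, life expectancy down to 3 months, and no active concurrent systemic therapy.

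There is no control arm to share this background. The observed proportion is tested against a fixed 0.6, so pain elsewhere enters the primary result directly. A disappointing rate could reflect SBRT that did not work or disease that progressed elsewhere, and the data as collected would not separate the two.

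The omission looks unintended, because the protocol does use a site qualifier in other places. The local-control outcome is defined on treated lesions, and the Background reports that patients in a retreatment trial "had reduced pain at the site of repeat radiation".

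**Working it through.** **1. How pain elsewhere moves a patient between classes.** Let B be the baseline BPI score. Suppose the treated site is pain-free at month 3 and the patient rates the pain that remains elsewhere, E. With no OME increase, the definitions give:

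- E = 0: complete response.
- E above 0 and at most B − 2: partial response. Overall response is unaffected, taking it as complete plus partial.
- E above B − 2 but at most B: response only if OME also falls by at least 25%.
- E above B but below B + 2: neither response nor failure.
- E at least B + 2: treatment failure.

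For B = 7, pain elsewhere up to 5 still leaves a partial response, 6 or 7 leaves only the OME route, 8 is a non-response, and 9 or 10 is a failure. At the entry floor, B = 2, B − 2 = 0. Any pain elsewhere of 1 or 2 then leaves only the OME route, 3 is a non-response, and 4 or more is a failure. Misclassification is thus conditional on a threshold, but patients who enter with low scores have little or no margin.

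Analgesia acts in the same way. Any OME increase, for whatever pain, blocks every route to response, and an increase above 50% is a failure.

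**2. The plan's own sample size.** The inputs, from the Sample size section, are p0 = 0.60, p1 = 0.80, two-sided alpha 0.05 and power 80%.

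- Arcsine formula: (1.960 + 0.842)² / (2·asin√0.80 − 2·asin√0.60)² = 40.15, rounded up to 41. This matches the protocol.
- Normal approximation: [(1.960·√0.24 + 0.842·√0.16) / 0.20]² = 42.04, rounded up to 43.

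The concern therefore does not rest on an error in the 41. With all 45 recruited patients evaluated, the exact test succeeds at 34 or more responders. The upper-tail probability at 0.60 is 0.0216 and the power at 0.80 is 0.826. At 41 patients the exact power is 0.704, which is a separate matter, so the illustration below uses 45.

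**3. Illustration of masking.** Two assumptions are needed, and the documents support neither: that the postulated 80% is a treated-site rate, and that a share m of those responders is masked by pain elsewhere. The observed rate is then 0.80 × (1 − m), and power is P(X ≥ 34 | 45, rate).

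| m | Observed rate | Exact power, n = 45 |
|---|---|---|
| 0% | 80% | 83% |
| 5% | 76% | 61% |
| 10% | 72% | 37% |
| 20% | 64% | 7% |

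At m = 25% the observed rate equals the null, 0.60.

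**4. The reverse error.** A patient whose treated site is unchanged can be credited with response if unrelated baseline pain improves. If a share f of the 20% treated-site non-responders is credited in this way, the observed rate is 0.80(1 − m) + 0.20f. The two errors cancel when 0.20f = 0.80m, that is f = 4m: 20% for m = 5%, and 40% for m = 10%. The documents give neither m nor f, so the net direction is open.

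**The case against.** The strongest reply is that the endpoint is named as overall pain response, and that both the 80% and the 60% may already describe overall pain. In that case no power is lost relative to the plan, and the null carries the same dilution. Scoring only the treated site against a whole-body benchmark would then create a mismatch that does not exist now. This stands as a limit on the power figures and on any claim of bias against the 60%. It does not reconcile the stated aim with the form.

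A reader might infer from the site-specific wording in the Background that the benchmark itself was measured at the treated site. The documents do not support that. The wording concerns a retreatment trial with response rates of 45% and 51%, and previously irradiated sites are excluded here. The 60% corresponds to the meta-analysis of palliative RT, for which the protocol does not say how pain was attributed.

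It can also be said that all bone lesions painful at entry are treated, that item 2 records location, and that a downward bias would be conservative. The first point narrows the problem to new lesions and non-bone pain. The second gives locations but no score for each site, and no rule uses them. The third holds only if the bias is in fact downward, which cannot be shown, and a conservative bias would still make a negative result hard to interpret.

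Finally, a treated-site BPI leaves OME as a whole-body quantity, so masking through analgesia would remain. That is correct, and the fix has to allow for it.

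**Conclusion.** The mismatch holds on the text: the aim concerns pain from treated bone lesions, but neither the instrument nor the response and failure criteria for pain carry a treated-site qualifier. Pain elsewhere can change a patient's class in either direction when it crosses a threshold. Size and net direction cannot be derived from the documents. The fall in exact power at 45 patients from 83% to between 61% and 37% is an illustration. It assumes that the 80% is a treated-site rate, that 5% to 10% of those responders are masked, that no error runs the other way, and that all 45 patients are evaluated.

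Two stronger readings should be resisted. One is that any new or unrelated pain counts as non-response or failure. It does not, because a sufficient BPI drop, or an OME reduction of at least 25% without a BPI rise, still gives a response. The other is that the trial is shown to be underpowered by these amounts, which would need a masking rate that the protocol does not contain.

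The point should be settled in the protocol rather than left to a later analysis plan. The protocol defines the endpoint and appends the form, and a treated-site score that was never asked for cannot be recovered afterwards.

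**What to change.** 1. Check how pain was attributed in the source of the 60% benchmark, state it, and match the endpoint to it.
2. Mark the treated site or sites on the item 2 diagram at baseline. At baseline and at 1, 3 and 6 months, instruct patients to rate pain at those sites. Prespecify a rule for patients with several sites, and define response on that score.
3. Limit the re-irradiation and fracture components of the failure definition to treated sites.
4. Keep the whole-body BPI rating as a supportive outcome.
5. Because OME stays whole-body, record the reason for any analgesic increase. Add a sensitivity analysis in which increases attributed to untreated sites do not block response.

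The cost is an instruction line on the questionnaire and telephone script, a case-report field for the treated site and one for the reason for an analgesic change. Asking for both ratings adds slightly to the burden on patients. The sample size need not change on this account. There are two downsides. Some patients cannot separate pain by site, and self-attribution in an unblinded single-arm study may favour SBRT. The supportive whole-body analysis would help to reveal the latter.
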